# Procedures to be Followed in the Event of Abnormal Laboratory Test Values or Abnormal Clinical Findings

## **Reporting Procedures**

Discarded blood samples from routine blood draws will be used for study measurements. No extra blood will be drawn from infants. This study does not involve any invasive procedures.

Any AE considered serious by the PI or Sub investigator or which meets the aforementioned criteria must be submitted on the SAE form to the IRB in accordance with IRB policies and procedures.

The study clinician will complete a Reportable Event Form within the following timelines:

- All serious adverse events described above to the UTMB IRB will be reported via InfoED utilizing the Reportable Event Form within 10 days.
- Serious adverse events involving an unexpected death or life-threatening experience related to research which be reported to the UTMB IRB within 2 days after first knowledge by the principal investigator.

All SAEs will be followed until satisfactory resolution or until the PI or Sub investigator deems the event to be chronic or the patient to be stable.

## 8.0 Study Withdrawal/Discontinuation

### **Reasons for Withdrawal**

A study subject will be discontinued from participation in the study if any of the following occur:

- Unacceptable toxicity or adverse event (AE): Drop in systemic mean blood pressure > 25% from baseline
- Unacceptable laboratory abnormalities: Thrombocytopenia < 50,000 not explained by other co-existing conditions
- Intercurrent illness, or other medical condition or situation occurs such that continued participation in the study would not be in the best interest of the subject in the opinion of the treating investigator, for e.g. necrotizing enterocolitis requiring subject to be made NPO.
- Development of any exclusion criteria
- Parents withdraw consent to continue in the research for any reason

### Handling of Withdrawals

Any subjects that withdraw from the study will continue to receive standard of care treatment according to our NICU protocols and will continue to be followed clinically by the primary neonatologist. Safety data from these subjects will be presented to the DSMB for evaluation.

Since this is a pilot study, we will not need to replace subjects in case of withdrawals.

## **Termination of Study**

Given the short duration of the trial, we do not plan to conduct any interim analyses or specify any early-stopping rules.

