**Safety of oral citrulline:** L-citrulline has been safely used for decades in patients with urea cycle defects. It has been used in pediatric patients with sickle cell disease and in infants undergoing cardiac surgery. No side effects were reported in these studies. In a study in newborn rats exposed to hyperoxia, L-citrulline caused a marked increase in arginase-2 expression in the lungs and this could have an impact on lung development and remodeling(5). However, this is only a theoretical risk.

Oral L-citrulline supplementation may prevent and/or decrease the severity of BPD\_PH. Since oral L-citrulline supplementation has never been studied in preterm infants before, the side effect profile and appropriate dosing is still unknown. In this pilot study, we will determine the safety profile, efficacy and appropriate dosing of oral Lcitrulline in preterm infants. In future, information from this study will be utilized to conduct a randomized placebo-controlled trial to evaluate the role of L-citrulline supplementation in treating BPD\_PH.

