### 4.0 Treatment Assignment/Randomization

**Recruitment** - Parents of all eligible infants will be approached by research investigator to discuss about the study & research protocol in detail. All questions & concerns will be answered in very simple language & parents will be given written consent form to read. Within 24 to 48 hours, the parents will be approached again to discuss & explain any question they have. We expect around 70 - 75% success in the recruitment. Every year, we deliver around 50 infants ( $\leq$ 30 weeks' gestation). We hope to recruit our desired sample of 42 infants (14 in each study group) within 12 months.

**Sample size:** 14 preterm infants will be randomized to each group (total sample 42) A sample size of 14 at each group (low, median, and high dose) for efficacy endpoint will reach a power of 0.80 to detect an effect size of 0.5 based on one-way ANOVA with a 0.05 significance level. A sample size of 11 at each group for safety endpoint will reach a power of 0.92 at a 0.05 significant level for an equivalence test of means using two onesided tests, when the true difference between the means is 0.0 mmHg, the standard deviation is 10.0 mmHg, and the equivalence limits are -15.0 mm Hg and 15.0 mmHg.

**Randomization:** Adaptive randomization method will be used – each new participant will be sequentially assigned to a particular treatment group by taking into account the previous assignments of participants. For example, first recruit will be Group 1, second Group 2, third Group 3, fourth Group 1 and so on. The study will be blinded to the nurses and parents. If patients complete 12/14 doses of the treatment, they will be analyzed in the treatment arm.

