### 9.0 Statistical Considerations

Study design: Single-center Pilot dose-ranging study

Study population: Premature infants admitted to the Neonatal intensive care unit at UTMB, Galveston.

Rationale: L-citrulline has been shown to increase NO production in neonatal pigs. The use of L-citrulline in premature infants may help increase NO and prevent pulmonary hypertension that develops due to chronic lung disease. Even though L-citrulline has been used safely in infants and children for urea cycle disorders, its dosage, efficacy and safety have not been evaluated in premature infants. Therefore, a pilot dose-ranging study is essential.

There will be 3 study groups in this Phase I trial:

Group 1 (Low dose): 100 mg/kg/day of L-citrulline Group 2 (Medium dose): 200 mg/kg/day of L-citrulline Group 3 (High dose): 300 mg/kg/day of L-citrulline

Sample size: A sample size of 14 at each group (low, median, and high dose) for efficacy endpoint will reach a power of 0.80 to

detect an effect size of 0.5 based on one-way analysis of variance (ANOVA) with a 0.05 significance level. The sample size calculation was based on the following expected mean  $\pm$  SD citrulline concentrations in plasma according to the study from Schwedhelm et al:

Low dose group:  $19 \pm 4 \ \mu mol/L$ Medium dose group:  $21 \pm 4 \ \mu mol/L$ High dose group:  $45 \pm 5 \ \mu mol/L$ 

Primary outcome:

1. Increase in plasma L-citrulline levels and increased NO production (measured indirectly via urinary breakdown products)

Secondary outcomes:

- 1. To determine safety of enteral L-citrulline supplementation in premature infants.
- 2. To determine the dose of enteral L-citrulline needed to increase plasma level of citrulline > 37 mol/L.

Data will be collected from electronic medical records. Measurements will be recorded in a password protected computer on an excel sheet.

A Data Safety Monitor Board (DSMB) as mentioned in section 7.0 will be reviewing safety data every 4 months.

The data will be analyzed at the end of data collection for all subjects who meet the inclusion criteria. SPSS version 24 will be used for data analysis. SAS procedures, linear models, repeated measures analysis of variance (ANOVA) & logistic modeling for receiver operator curve generation (significance p<0.05) will be used. The UTMB Clinical trials studio will be involved to assist in statistics.

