# 11.0 Record Retention

The expected duration of this study is 1 year,

Since this research study accesses protected health information (PHI) and is covered under the Health Insurance Portability Accountability Act (HIPAA), consent forms that

include the HIPAA Authorization are to be retained for a minimum of 6 years from the date of the authorization.

Since this Research involves pediatric subjects, records shall be maintained until the last participating subject reaches age 21 or 10 years after completion of the research, whichever is later.

Research records will be maintained in accordance with the current version of the Texas Health Records Table 17-III Record Retention Schedule, Human Subject Research Records and Documents.

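### Short duration is not a sound reason for having no stopping rule: accrual takes 12 to 14.4 months, and a per-dose safety pause would be a cheap, modest improvement

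*Combined protocol and SAP*

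**What the plan says.** Section 8.0, Termination of Study: "Given the short duration of the trial, we do not plan to conduct any interim analyses or specify any early-stopping rules". No other reason is given.

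On time scale, each course lasts 7 days (section 2.0, Aim 3). Section 11.0 states: "The expected duration of this study is 1 year". Section 4.0 adds "We hope to recruit our desired sample of 42 infants (14 in each study group) within 12 months", from about 50 eligible births a year, and "We expect around 70 - 75% success in the recruitment".

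On exposure, section 9.0 says "There will be 3 study groups in this Phase I trial", and section 1.0 notes that "oral L-citrulline supplementation has never been studied in preterm infants before". Section 4.0 assigns doses in strict rotation ("first recruit will be Group 1, second Group 2, third Group 3, fourth Group 1 and so on"), so every third infant receives the highest dose from the outset.

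Safeguards exist:
- A DSMB "will be reviewing safety data every 4 months" (section 9.0).
- An infant whose MAP falls by more than 25% is taken off study, and safety data on withdrawn infants go to the DSMB (section 8.0).
- Serious events, including any the investigator considers serious, are reported to the IRB within 2 or 10 days (section 7.0).
- Section 6.0, under the heading on modification for a participant, says toxicity leads to the study being stopped and refers to section 7.0. It gives no number of events.

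Hypotension is a listed serious event only when two or more inotropes are needed (section 7.0). The fall above 25% that section 8.0 treats as unacceptable toxicity does not reach that list by itself.

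**The concern.** A stopping rule is impractical when most participants have been treated before any outcome is known. Here the reverse holds. Outcomes arrive within days while enrolment runs for a year or more, so a short course makes a rule easier to apply.

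At stake is how many further infants start a dose that is already causing hypotension. Withdrawing the affected infant does not stop the next infant in the rotation from starting the same dose. With three doses opened together and no escalation, no earlier cohort shows that the lower doses are tolerated before the highest is given. What the plan declines is a count, fixed in advance, at which a dose is paused whatever the review calendar.

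**Working it through.** **Plan's own figure.** One-way ANOVA with 3 groups of 14, f = 0.5 and alpha 0.05 has noncentrality 42 × 0.25 = 10.5 and power 0.803, matching the stated 0.80. A safety-only pause spends no alpha and leaves this unchanged unless a group closes.

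**Accrual (section 4.0).**
- At 70% consent: 50 × 0.70 = 35 a year; 42/35 × 12 = 14.4 months.
- At 75%: 37.5 a year; 42/37.5 × 12 = 13.4 months.
- Finishing in 12 months needs 42/50 = 84% of births.

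**Infants between DSMB reviews.** 35/3 = 11.7 to 42/3 = 14 per 4 months, which is 3.9 to 4.7 per dose. Over 121.7 days that is one start per dose every 26 to 31 days. With a 7-day course, 3.89 × 7/121.7 = 0.22 to 4.67 × 7/121.7 = 0.27 infants per dose are on drug at any time. An event would therefore usually be known before the next start at that dose.

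**Event rates.** The documents give none, so every rate p below is an assumption. In this part every MAP fall above 25% is counted.

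*Hold probability for one dose,* X ~ Bin(14, p):

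| p | P(X ≥ 2) | P(X ≥ 3) |
|---|---|---|
| 5% | 0.153 | 0.030 |
| 10% | 0.415 | 0.158 |
| 20% | 0.802 | 0.552 |
| 30% | 0.953 | 0.839 |

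*At least one false hold in three groups,* 1 − (1 − P)³:
- 2nd-event rule: 39% at a 5% background rate, 80% at 10%.
- 3rd-event rule: 9% and 40%.

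The 2nd-event rule detects more but pauses too readily if background falls are common, so the 3rd event is the better starting point.

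*Expected infants treated of 14, 3rd-event rule.* Counting continuously: the sum over n = 0 to 13 of P(Bin(n, p) ≤ 2). The comparator is a DSMB that stops the dose at the first scheduled review with 3 or more events, with reviews after 4/8/12 or 5/10 infants per dose. For example, at 20% with reviews at 4/8/12: 4 + 4(0.973) + 4(0.797) + 2(0.558) = 12.20.

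| p | Continuous | DSMB reviews only | Fewer treated |
|---|---|---|---|
| 10% | 13.45 | 13.61–13.68 | 0.16–0.23 |
| 20% | 11.55 | 12.20–12.42 | 0.65–0.87 |
| 30% | 9.28 | 10.38–10.72 | 1.09–1.43 |

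*Before the first review* (4 or 5 infants per dose), the chance of two or more events is 18–26% at a 20% rate and 35–47% at 30%. The chance of three or more, from the same binomials, is 3–6% and 8–16%. The 3rd-event rule therefore acts mostly after the first review.

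**Effect of attribution.** If only drug-associated falls count and 80% of toxic falls are so judged (assumed), the counted rates are 0.16 and 0.24. The 3rd-event hold probability drops from 55% to 39% and from 84% to 69%. False holds also fall, by an amount that depends on how many background falls are attributed to the drug.

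**Power if a group closes for good at 9.** Take equally spaced means −d, 0, d at f = 0.5 (d² = 0.375 in SD² units) and close an outer group. Noncentrality = 23 × 0.375 − 37 × (5/37)² × 0.375 = 8.37, and power is about 0.70.

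**The case against.** The best defence is that the plan already has layered protection: individual withdrawal, a DSMB, IRB reporting in days, and a section 6.0 statement that toxicity stops the study. Earlier use in other populations is reported without side effects (sections 1.0 and 7.0), and a one-year, 42-infant, single-centre pilot can fairly be called short.

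Much of this stands. The safeguards are real, the benefit depends on assumed rates, and at a 10% event rate it nearly vanishes. The comparator assumes nobody acts between reviews. The upper first-review figures use 5 infants per dose, slightly above the 4.7 maximum. With only 3 per dose treated by then, the chance of two events is 10% at a 20% rate and 22% at 30%. The rule also leaves out platelets below 50,000, the other named withdrawal criterion, although that is already a listed serious event.

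It does not rescue the stated reason. Even if a year is short, two or three DSMB reviews fall within accrual, so there is time to act.

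A reader might infer that the trial has no means of pausing a dose. The documents do not support that. Part of section 7.0, where section 9.0 places the DSMB description, is not in the text available, and section 6.0 refers to section 7.0 for the response to toxicity. Section 6.0 may mean only stopping that infant's treatment. Read literally, it conflicts with section 8.0, which is a reason to reconcile the two.

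**Conclusion.** The reason given in section 8.0 does not fit the trial. That part needs no assumed event rate; it follows from the plan's own durations, recruitment figures and review interval. The accrual arithmetic ignores exclusions and infants lost before they come off parenteral nutrition, which would lengthen accrual and lower the number per interval.

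Adding a dose-level pause is an improvement to consider, not the repair of a serious defect. The size in infants spared assumes that every fall is counted, that each is known before the next start at that dose, and that the DSMB would otherwise act on the same count at its scheduled reviews. It would be a mistake to read the hold probabilities as the operating characteristics of the attributed rule. Attribution lowers them, and the protocol gives no basis for saying by how much.

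**What to change.** Replace the Termination of Study sentence with text such as:

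> No interim efficacy analysis is planned. Each withdrawal for a MAP fall of more than 25% judged associated with study drug is counted by dose group as it occurs. At the 3rd such event in a dose group, new starts at that dose pause for unscheduled DSMB review, and assignment rotates among the groups still open.

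First check this against the complete DSMB text in section 7.0. If a dose-level hold already exists there, correct the reason in section 8.0 and make the sections agree. Reword section 6.0 to say whether toxicity stops the infant's treatment, the dose or the study. The DSMB should confirm the count from a one-page binomial table that includes a range of attribution rates, and decide whether low platelets should also count.

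The trigger is already recorded and graded, and association is already defined in section 7.0, so no new data, efficacy look or alpha adjustment is needed. The costs are:
- false pauses, at the rates shown above;
- temporary imbalance in the rotation while a group is held;
- if an outer group closes for good, lower ANOVA power: about 0.70 at 14/14/9 against 0.80 planned, since withdrawals are not replaced.

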### 9.0 Statistical Considerations

Study design: Single-center Pilot dose-ranging study

Study population: Premature infants admitted to the Neonatal intensive care unit at UTMB, Galveston.

Rationale: L-citrulline has been shown to increase NO production in neonatal pigs. The use of L-citrulline in premature infants may help increase NO and prevent pulmonary hypertension that develops due to chronic lung disease. Even though L-citrulline has been used safely in infants and children for urea cycle disorders, its dosage, efficacy and safety have not been evaluated in premature infants. Therefore, a pilot dose-ranging study is essential.

There will be 3 study groups in this Phase I trial:

Group 1 (Low dose): 100 mg/kg/day of L-citrulline Group 2 (Medium dose): 200 mg/kg/day of L-citrulline Group 3 (High dose): 300 mg/kg/day of L-citrulline

Sample size: A sample size of 14 at each group (low, median, and high dose) for efficacy endpoint will reach a power of 0.80 to

detect an effect size of 0.5 based on one-way analysis of variance (ANOVA) with a 0.05 significance level. The sample size calculation was based on the following expected mean  $\pm$  SD citrulline concentrations in plasma according to the study from Schwedhelm et al:

Low dose group:  $19 \pm 4 \ \mu mol/L$ Medium dose group:  $21 \pm 4 \ \mu mol/L$ High dose group:  $45 \pm 5 \ \mu mol/L$ 

Primary outcome:

1. Increase in plasma L-citrulline levels and increased NO production (measured indirectly via urinary breakdown products)

Secondary outcomes:

- 1. To determine safety of enteral L-citrulline supplementation in premature infants.
- 2. To determine the dose of enteral L-citrulline needed to increase plasma level of citrulline > 37 mol/L.

Data will be collected from electronic medical records. Measurements will be recorded in a password protected computer on an excel sheet.

A Data Safety Monitor Board (DSMB) as mentioned in section 7.0 will be reviewing safety data every 4 months.

The data will be analyzed at the end of data collection for all subjects who meet the inclusion criteria. SPSS version 24 will be used for data analysis. SAS procedures, linear models, repeated measures analysis of variance (ANOVA) & logistic modeling for receiver operator curve generation (significance p<0.05) will be used. The UTMB Clinical trials studio will be involved to assist in statistics.

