## 3.0 Inclusion/Exclusion Criteria

Inclusion criteria - Subjects must meet all of the inclusion criteria in order to be eligible to participate in the study.

1. Infants  $\leq$  30 weeks' gestational age born at UTMB, Galveston.

2. Parents have provided informed consent/assent in a manner that is approved by the IRB

The reason for the inclusion of such a vulnerable population is that BPD is primarily a disease of premature infants and PH is a common complication of BPD. It is also a condition with high mortality and there still exists significant confusion over appropriate management. Being a randomized controlled trial, the study does add certain risks to the subjects: frequent blood draws (minimized by using discarded blood and urine samples) . Since diagnosis and management of BPD\_PH is not currently standard of practice, we will not be withholding any beneficial therapy. The present research protocol will not interfere in the management of the preterm infants as treating neonatal team will be taking all management decisions. All risks will be explained to the parents and written informed consent will be obtained from the parents of all subjects.

Exclusion criteria - Subjects meeting any of the exclusion criteria at baseline will be excluded from study participation.

1. Known congenital or chromosomal anomalies.

2. Congenital heart disease affecting cardio-respiratory system (other than PDA, PFO or ASD)

3. NEC, sepsis, or any condition requiring surgery prior to recruitment

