## Dose of study drug -

Low dose 100 mg/kg/day Medium dose 200 mg/kg/day High dose 300 mg/kg/day

[figure not shown]
**When to start study drug -** Study drug will be started when infant has been off of TPN for at least 3 days so that IV arginine in TPN does not interfere.

**Sample collection** - 1 mL of blood will be collected from each subject at 2 time points: before starting citrulline (Day 0) and then after completing 1 week enteral L-citrulline supplementation (Day 7). Discarded blood sample from routine blood draw will be used.

It is standard of care for all preterm infants to get weekly blood draws on Tuesdays for hemoglobin monitoring. We will use discarded blood sample from the Tuesday after being on full feeds (no TPN) and start enteral L-citrulline supplementation on the first Tuesday (Day 1) after off TPN for at least 3 days. After 1 week, supplementation will be discontinued (last dose Monday PM) and discarded blood sample from Tuesday (Day 7) will be used to analyze plasma levels or L-citrulline and L-arginine. Immediately after blood collection, blood will be centrifuged at 4-degree C to extract serum. Serum will be divided into aliquots of 100 microliter & stored at -80-degree C for future use.

1 mL of urine will be collected before starting (Day 0) and then daily thereafter till the last day of L-citrulline supplementation (Day 7). Urine will be collected by placing cotton balls in diapers at around noon  $\pm$  2 hours (in between the 2 doses of study drug).

All sample collection will be part of routine/standard care of the infant and no extra blood draws/invasive procedures will be needed.

Sample collected - (time points)

- \*Discarded blood (for arginine, citrulline & ADMA)
- ^Urine daily for urinary arginine, citrulline, nitrites and nitrates

**\*Enteral L-citrulline** –low, medium or high dose divided into 2 doses via gavage feeding tube i.e. 10% L-citrulline twice daily.

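### The citrulline means given as the basis for 14 per group imply an effect size f of about 2.7, not 0.5, and the recruitment figures give about 35 to 37.5 infants in 12 months, not 42

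*Combined protocol and SAP*

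**What the plan says.** **Sample size.** Section 4.0 (Sample size) states that 14 infants per dose group "will reach a power of 0.80 to detect an effect size of 0.5 based on one-way ANOVA with a 0.05 significance level". Section 9.0 repeats this and adds the source: "The sample size calculation was based on the following expected mean". It then lists plasma citrulline by dose group, attributed to a published pharmacokinetic study: low 19 (SD 4), medium 21 (SD 4), high 45 (SD 5) µmol/L.

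**What the calculation has to cover.** The primary outcome in section 9.0 is "Increase in plasma L-citrulline levels and increased NO production (measured indirectly via urinary breakdown products"). The analysis text in the same section names plasma arginine and citrulline and urinary nitrite and nitrate as primary variables. It compares the three groups by one-way ANOVA and uses paired t-tests for pre-to-post change. Expected values are given for citrulline only.

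**Recruitment.** Section 4.0 (Recruitment) says: "We expect around 70 - 75% success in the recruitment. Every year, we deliver around 50 infants" of 30 weeks' gestation or less. It continues: "We hope to recruit our desired sample of 42 infants (14 in each study group) within 12 months". Section 11.0 states: "The expected duration of this study is 1 year". Section 3.0 adds that "Subjects meeting any of the exclusion criteria at baseline will be excluded from study participation". Section 8.0 does not replace withdrawals, and no allowance for losses is stated.

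**The concern.** A sample-size statement should let a reader go from the planning values to the stated power. Here the planning values are three means differing by up to 26 µmol/L with SDs of 4 to 5, and the effect size is 0.5. Those two do not look compatible. If they are not, the reader cannot tell what effect the trial was sized for, or how much loss it can tolerate. A reader may also take the citrulline means as support for the other primary variables, for which nothing is given.

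Recruitment bears on this. At f = 0.5 the design has almost no slack below 42 infants; at f of about 2.7 it has a great deal. Section 4.0's own figures seem to produce fewer than 42 infants in the stated year, so whether that matters for power depends on which basis is meant.

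**Working it through.** **Inputs.** Three groups of 14 (N = 42), alpha 0.05, one-way ANOVA, effect size 0.5, power 0.80, and the means and SDs above (sections 4.0 and 9.0). About 50 births a year, about 70 to 75% success, 42 infants in 12 months (section 4.0). Duration 1 year (section 11.0).

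**1. The plan's own figure.** Noncentral F with 2 and N − 3 degrees of freedom and noncentrality N × f². For f = 0.5 and N = 42, the noncentrality is 42 × 0.25 = 10.5 and power is 0.803. The stated 0.80 therefore reproduces if 0.5 is Cohen's f. Read as f², 0.5 gives power 0.983; read as eta-squared (f = 1), it gives more than 0.999. Neither matches 0.80.

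**2. The effect size implied by the listed means.**
- Grand mean: (19 + 21 + 45)/3 = 28.33.
- SD of the three means: √[((−9.33)² + (−7.33)² + 16.67²)/3] = 11.81.
- Pooled within-group SD: √[(16 + 16 + 25)/3] = √19 = 4.36.
- f = 11.81/4.36 = 2.71. With SD 4 throughout, 11.81/4 = 2.95; with SD 5 throughout, 11.81/5 = 2.36.
- SD needed for these means to give f = 0.5: 11.81/0.5 = 23.6 µmol/L, about five times the stated SDs.

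**3. Power at the implied effect size.**

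| Infants per group | f = 2.71 | f = 2.36 |
|---|---|---|
| 2 | 0.907 | 0.826 |
| 3 | 0.9999 | 0.998 |

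At f = 2.71 and 14 per group, power is 1.00 to two decimals. The listed means therefore cannot be what led to 14.

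**4. Recruitment.**
- Expected in 12 months: 50 × 0.70 = 35; 50 × 0.75 = 37.5.
- Success needed for 42 in 12 months: 42/50 = 84%.
- Time to 42: 12 × 42/37.5 = 13.44 months at 75% (13.5 when rounded up); 12 × 42/35 = 14.4 months at 70%.
- These figures treat every birth as eligible. The documents give no exclusion rate. If 90% were eligible (an assumption, for illustration), 12 months would give 31.5 to 33.75 infants, and 42 would take 14.9 to 16.0 months.

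**5. Power at f = 0.5 with fewer infants (before losses).**

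| N | Power |
|---|---|
| 42 | 0.803 |
| 41 | 0.792 |
| 37 | 0.743 |
| 36 | 0.729 |
| 35 | 0.715 |

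**6. Adjusting for the Day 0 value.** ANCOVA raises f to f/√(1 − r²), where r is the Day 0 to Day 7 correlation, and costs one degree of freedom. The documents do not give r. At N = 42 and f = 0.5, assumed r of 0.1, 0.3 and 0.5 give power 0.807, 0.840 and 0.906, against 0.803 for an unadjusted Day 7 ANOVA.

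**The case against.** The strongest reply is that little turns on this. With 42 evaluable infants the overall citrulline test has power of at least 0.80 on either basis. The mismatch errs in the safe direction for that test, and this is a pilot. That stands: 14 per group need not change, and the fall from 0.803 to 0.792 at 41 infants is trivial in itself. What does not stand is the sentence of provenance, which is wrong as written.

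On recruitment, section 4.0 uses approximate figures and expresses a hope, and nothing in the plan stops enrolment at 12 months. That also stands. The 35 to 37.5 is an approximate expectation, and the powers of 0.72 to 0.74 apply only if enrolment is in fact closed at 12 months. The likelier cost is 1.5 to 2.4 extra months. The approximations still do not turn 70 to 75% into 84%.

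A reader might go further in three ways that the documents do not support:
- That 0.5 came from the low-versus-medium difference, (21 − 19)/4, and that the trial is therefore underpowered to separate those doses. No text links the two figures. The plan has no pairwise dose test: section 9.0 has the overall ANOVA and paired t-tests, and Aim 3 asks which dose exceeds 37 µmol/L.
- That the parenteral-nutrition condition cuts the recruitment count further. The text, "Study drug will be started when infant has been off of TPN for at least 3 days", sets when dosing begins, not who is recruited.
- That the trial needs more infants, or far fewer. The finding is that the basis is unexplained. The very high power covers citrulline only.

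It can also be said that ANCOVA repairs neither inconsistency. That is right, so it is offered only as a separate improvement. Section 9.0 can be read as comparing Day 7 values or change from Day 0. On either reading, adjustment for Day 0 is at least as precise, apart from the one degree of freedom.

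**Conclusion.** Both inconsistencies hold on the plan's own numbers.

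**Basis of the sample size.** The stated power of 0.80 is correct for f = 0.5. The means said to underlie it imply f of about 2.7 (2.36 to 2.95), so the two cannot both be the basis. This rests on reading 0.5 as Cohen's f, the only reading tried that returns 0.80, and on taking the listed SDs as within-group SDs, as section 9.0 labels them. It does not show that the trial is too small for citrulline. It leaves the source of 0.5 unstated, and arginine and urinary nitrite and nitrate without any planning values.

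**Recruitment.** The expected number in 12 months is about 35 to 37.5 before exclusions, which is 4.5 to 7 short of 42. The plan does not say whether the gap would be met by more time or by fewer infants. Only the second affects power, and then only materially if f = 0.5 is the intended basis.

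This should be corrected before the plan is relied on. It is a definite error in the justification and timeline, cheap to repair, and not a threat to the design.

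**What to change.** 1. **Section 9.0, Sample size.** Replace the sentence that ties the calculation to the listed means with a statement that 14 evaluable infants per group (42 in total) gives power 0.80 for Cohen's f = 0.5. The sponsor should state where 0.5 comes from. Add that the listed citrulline means imply f of about 2.7 (overall power about 1.00), that this applies to citrulline only, and that no expected values are given for arginine or urinary nitrite and nitrate.

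2. **Sections 4.0 and 11.0.** Choose one of two restatements. Either give the time to recruit 42 as about 13.5 months (75% success) to 14.4 months (70%), longer once exclusions are counted, and extend the study duration to match. Or, if enrolment is to end at 12 months, give the expected number as about 35 to 37, with power of about 0.72 to 0.74 at f = 0.5 before losses.

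3. **Section 9.0, analysis (a separate improvement).** Compare the dose groups on Day 7 citrulline by ANCOVA with Day 0 citrulline as covariate, keeping the overall dose test. State that the gain depends on a correlation the plan does not give.

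**Cost.** Wording changes and no extra infants. Item 2 costs either about 1.5 to 2.4 more months of recruitment or a lower stated number and power. Item 3 uses the Day 0 sample already collected and one degree of freedom.
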